DIETARY ADJUSTMENT	
High tyramine-containing foods will be avoided:
 
 • Sausages, salami, pickled herring • Fava beans • Tap beers, non-pasteurized beers • Sauerkraut, yeast extract, soybean products including soy sauce • Aged cheeses
DRUG DOSAGE AND FORMULATION	
Subjects will take one 0.5 mg dosage Rasagiline tablet or the matching placebo once a day orally from Baseline visit to Week 4 visit. The dose will be titrated to one 1 mg dosage tablet or the matching placebo once a day starting on Week 5 through Week 24.

DURATION OF PARTICIPATION	
This is a 34-week study comprised of 7 in-clinic visits

PLACEBO	
A matching oral placebo will be used

ROUTE OF ADMINISTRATION	
Oral

PROCEDURES	
Physical and neurological exam, MRI, [18F]-FDG PET, ¹⁸F-AV-1451 Tau PET, ECG, vitals, clinical laboratory tests, MMSE, ADAS-Cog 11, CGIC, NPI, ADCS-ADL, Digit Span, COWAT, QoL-AD/Study Partner

STATISTICAL CONSIDERATION	
Intent-to-Treat (ITT) - The primary FDG analysis will include all patients who received both a screening and end of study scan of acceptable quality.
 
Modified Intent-to-Treat (mITT) – All randomized subjects who have been dispensed study medication and have one post-baseline visit during the blinded phase of the study.
 
Per-protocol (PP) population – All ITT subjects who complete the study (Week 24) and have ingested between 80% to 120% of the prescribed study medication as measured by pill count.
 
Observed case – An observed case analysis of all patients completing the study will be conducted.
 
Last Observation Carried Forward (LOCF) – Clinical data imputation will use the LOCF approach for missing patients.
 
Responder analysis – Responders will be defined as those that have a significant improvement on brain metabolism on FDG for the whole brain or for any of the pre-specified regions.
 
A secondary analysis will compare the changes in FDG at 24 weeks compared to the projected expected metabolism based on the Baseline FDG findings.

ADVERSE EVENTS	
SAFETY
 
Orthostatic vital signs, ECG, hematology, chemistry, TSH, B12 and urinalysis (UA) collected at Screening and at end of study

	
TOLERABILITY
 
Side effects data will be collected and converted to systems data using a data dictionary.
 
DSMB No Independent DSMB is required.

--	--

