11.2 Statistical Methods

Intent-to-Treat (ITT) - The primary FDG analysis will include all patients who received both a screening and end of study scan of acceptable quality. The primary clinical analysis will be a modified Intent-to-Treat (mITT) approach including all patients randomized and receiving at least one post-baseline assessment.

Per-Protocol (PP) population – All Intent-to-Treat subjects who complete the study (Week 24) and have ingested between 80% and 120% of the protocol prescribed study medication as measured by pill count.

Observed case – An observed case analysis of all patients completing the study will be conducted.

LOCF – Clinical data imputation will use the LOCF approach for missing patients

Responder analysis – Responders will be defined as those that have a significant improvement on brain metabolism on FDG for the whole brain or for any of the pre-specified regions.

A secondary analysis will compare the changes in FDG at 6 months compared to the projected expected metabolism based on the Baseline FDG findings.

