BIostatISTICS
RESEARCH CENTER

ALZHEIMER'S DISEASE COOPERATIVE STUDY (ADCS)

Rasagiline Rescue in Alzheimer's Disease (RAS) Clinical Trial Statistical Analysis Plan (SAP) – DRAFT

CONFIDENTIAL DOCUMENT

September 9, 2014

Investigators: [name] and [name]

Written by: ADCS RAS Biostatistics Team

Contents

| | |
|--|-----------|
| 1 Introduction | 3 |
| 2 Study Design | 3 |
| 3 Study Objectives and Hypotheses | 3 |
| 3.1 Primary Objectives | 3 |
| 3.2 Secondary Objectives | 3 |
| 4 Populations of Interest | 4 |
| 5 Analyses Populations: Definitions | 4 |
| 6 Enrollment and Participant Flow | 5 |
| 6.1 Accrual of the study | 5 |
| 6.2 Study Flow CONSORT Diagram | 5 |
| 6.3 Premature Discontinuation of Study Evaluation | 5 |
| 7 Evaluation of Demographics and Baseline Characteristics | 6 |
| 8 Imaging Analysis (Extracted from the protocol) | 7 |
| 8.1 Screening Classification | 7 |
| 8.2 Screening Characterization | 7 |
| 8.3 Longitudinal Voxel-Based Evaluation | 7 |
| 8.4 Longitudinal Region of Interest based Evaluation | 7 |
| 9 Analysis of Clinical Measures | 8 |
| 10 Correlation between Imaging and Clinical Change | 8 |
| 11 Evaluation of Safety Measures | 9 |
| 12 Software | 10 |
| 13 References | 10 |

1 Introduction

This document outlines the Statistical Analysis Plan (SAP) for the *Rasagiline Rescue in Alzheimer's Disease Clinical Trial*.

2 Study Design

This is a Phase II, randomized, double blind, placebo controlled, parallel group, proof of concept three-site study, to evaluate the effect of Rasagiline in the regional brain metabolism on FDG PET. The study consists of two phases: a 24 week double blind placebo controlled treatment period and a 4 week follow up period. Patients will be randomized in a 1:1 ratio at baseline to receive either Rasagiline or matching placebo.

The study drug will be given as 0.5 mg dose once daily for the 4 weeks, then increases to 1 mg daily for the next 20 weeks. A total of 50 subjects will be enrolled: 25 will receive Rasagiline and 25 will receive matching placebo for the 24-week treatment period.

3 Study Objectives and Hypotheses

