3.2 Secondary Objectives

- To evaluate the efficacy of Rasagiline 1 mg once daily compared to placebo after 24 week treatment on cognition (ADAS-cog), activities of daily living (ADCS-ADL), global function (CIBIC+), and neuropsychiatric symptoms (NPI)
- To evaluate the efficacy of Rasagiline 1 mg once daily compared to placebo after 24 week treatment on measures of executive function (mazes and cancellation of the ADAS-Cog13, Digit Span test, and Controlled Oral Word Association Test [COWAT] for verbal fluency)
- To evaluate the safety and tolerability of Rasagiline as measured by incidence of adverse events/serious adverse events (AEs/SAEs) clinical lab test data, vital signs, 12 lead EKG data, brain MRI finding

4 Populations of Interest

- Intent-to-Treat (ITT) Population: All consented randomized subjects grouped according to the treatment assigned at randomization, regardless of any protocol violations or any crossovers.
- Per-Protocol (PP) Populations: All Intent-to-Treat subjects who meet the inclusion criteria and exclusion criteria specified for enrollment in the protocol, and complete the study (week 24), have ingested between 80% and 120% of the protocol prescribed study medication as measured by pill count, and with no protocol violations that affect the analysis.

5 Analyses Populations: Definitions

- FDG Analyses: The primary FDG analysis will include all patients who received both a screening and end of study scan of acceptable quality.
- Clinical Outcome Analyses: The primary clinical analyses will include the ITT population.
- Safety Analyses: The primary clinical analyses will include the ITT population.
- Responder analysis: Responders will be defined as those that have a significant improvement on brain metabolism on FDG for the whole brain or for any of the pre-specified regions.

6 Enrollment and Participant Flow

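### Secondary clinical endpoints: the protocol's mITT set with LOCF and the draft SAP's all-randomised mixed model or GEE are not reconciled, and neither document says which governs

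*Protocol*

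**What the plan says.** **Protocol.** Section 11.2 sets the clinical population: "The primary clinical analysis will be a modified Intent-to-Treat (mITT) approach including all patients randomized and receiving at least one post-baseline assessment". The Synopsis defines mITT slightly differently: "All randomized subjects who have been dispensed study medication and have one post-baseline visit during the blinded phase of the study". Both places give LOCF as the imputation rule ("Clinical data imputation will use the LOCF approach for missing patients") and both add an observed-case analysis of completers with no stated rank. No model or test is named for the clinical scales. Section 3.4 defines the endpoints as change from Baseline to Week 24.

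**SAP.** The title page reads "Statistical Analysis Plan (SAP) – DRAFT" and is dated September 2014. Section 4 defines ITT as "All consented randomized subjects grouped according to the treatment assigned at randomization", with no post-baseline condition. Section 5 states: "Clinical Outcome Analyses: The primary clinical analyses will include the ITT population". Section 9 fits a linear mixed model to MMSE, ADAS-Cog 11, ADCS-ADL, NPI, Digit Span, COWAT and QoL, with time continuous and the time-by-treatment term as the test. Response profiles (time categorical) are the sensitivity analysis, CGIC is dichotomised and analysed by GEE, and the analyses are repeated in the per-protocol set. The words mITT, LOCF, observed case and imputation do not occur in the SAP.

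The SAP is only partly updated. Section 3.2 still names CIBIC+ and "mazes and cancellation of the ADAS-Cog13", while section 9 uses CGIC and ADAS-Cog 11.

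**Schedule.** ADAS-Cog 11, ADCS-ADL, NPI, Digit Span and COWAT are scored at Weeks 4, 8, 24 and 28; CGIC at Weeks 4, 24 and 28. MMSE and QoL-AD have one post-dosing score, at Week 24 (8.1.1, 8.2.6). Patients who withdraw are asked back for Visit 6 (5.4), whose battery contains neither MMSE nor QoL-AD (7.6, Table 2).

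**The concern.** The population and the missing-data rule differ between the two documents, and no clause gives either precedence. That leaves room to settle the main clinical analysis after results are seen. SAP section 9 already makes no multiplicity adjustment and lets exploratory analyses guide the efficacy analyses.

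The choice also affects the result. Where patients decline over 24 weeks, carrying an early score forward flatters the arm that loses more patients. With equal dropout, it shrinks a difference that grows with time. For MMSE and QoL-AD the protocol rule is also incomplete: a patient who leaves after Week 4 belongs to the mITT set but has no post-baseline score to carry. LOCF must then either use the baseline score, which means zero change, or omit the patient. The protocol does not say which.

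**Working it through.** **Plan's own figures.** Neither document gives a sample size, SD, decline or dropout rate for the clinical endpoints, so there is nothing to reproduce. The inputs below, other than 25 per arm and the visit weeks, are assumptions.

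**The two rules side by side**

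| Item | Protocol (Synopsis, 11.2) | Draft SAP (4, 5, 9) |
|---|---|---|
| Set | mITT, post-baseline data required | All randomised |
| Missing data | LOCF | No rule stated; likelihood model or GEE |
| Other analyses | Observed case (unranked), PP | Response profiles (sensitivity), PP |
| Target | Change to Week 24 | Rate of change over 24 weeks |

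The set matters less than the missing-data rule, because patients with only a baseline score add little to a time-by-treatment estimate.

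**MMSE, unequal dropout, no true effect, baseline carried.** Assume 6 vs 2 dropouts of 25 (24% vs 8%), change SD 3 and decline D in both arms.
- Spurious difference = (0.24 − 0.08) × D = 0.16, 0.32, 0.48 for D = 1, 2, 3.
- Simulated two-sided rejection by t-test: 5.2%, 6.1%, 7.2%. With D = 0 the difference is 0.00 and the rate 5.0%.
- Observed cases under the same random dropout: no bias, rejection about 5%.
- A mixed model on the two time points, with covariances chosen to give change SD 3, also shows a mean difference of about 0.00. This follows from the assumed random dropout.

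**Precision in the same setting.** Mean SE is 0.78 to 0.83 for LOCF (D = 1 to 3), 0.92 for observed cases and 0.92 to 0.93 for the mixed model. Ratios: 0.92/0.83 = 1.11 and 0.93/0.78 = 1.19.

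**MMSE, equal dropout d, true difference 1.0, baseline carried.** The estimate becomes 1.0 × (1 − d) = 0.92 at 8% and 0.76 at 24%. The SE shrinks too, so simulated power changes less:
- 8% dropout: 19.5%, 19.3%, 17.9% (D = 1, 2, 3) against about 19.6% for observed cases.
- 24% dropout: 16.8%, 15.3%, 13.1% against about 17%.

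The loss is about 0 to 4 percentage points.

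**ADAS-Cog, last score at week t.** Assume linear decline of 2 to 4 points and 24% vs 8% dropout.
- Spurious difference = decline × (1 − t/24) × 0.16. Smallest: 2 × (1 − 20/24) × 0.16 = 0.05. Largest: 4 × (1 − 4/24) × 0.16 = 0.53.
- With equal dropout, a linearly growing effect keeps 1 − d × (1 − t/24) of its size: from 1 − 0.24 × 20/24 = 0.80 to 1 − 0.08 × 4/24 = 0.99.
- An effect present by Week 4 and then stable keeps all of it.

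No figure was calculated for CGIC.

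**The case against.** The strongest reply is that there are not clearly two rules in force. The SAP is an unadopted draft, partly out of date, and it omits LOCF by silence. The protocol kept LOCF through Amendment 5 and names no clinical model that the SAP could contradict. This stands as a limit on the claim: the direct conflicts are the analysis set and the missing-data rule. It does not remove them, since the documents do not say how the draft relates to the protocol.

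A reader might infer that the protocol itself favours the SAP approach, because section 5.5 follows withdrawn subjects and section 9.2 keeps data for an intent-to-treat analysis. The text does not support that. Section 9.2 concerns medication restrictions, section 5.5 sets no Week 24 clinical assessment, and a single Visit 6 score is equally compatible with LOCF.

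A reader might also infer that LOCF seriously distorts the clinical results. That is not supported either. MMSE and QoL-AD are listed endpoints but are not named in the section 3.2 objectives; every scale named there is in the Visit 6 battery. If MMSE dropouts are omitted and dropout is random, there is no bias. Section 1.5 allows for a symptomatic effect, and if that appears early and stays stable LOCF loses nothing.

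**Conclusion.** The point holds as an unreconciled analysis rule with a modest, conditional bias. For MMSE the spurious difference is 0.16 to 0.48 points and the false-positive rate about 5% to 7%. Those figures rest on assumed unequal dropout (24% vs 8%), a decline of 1 to 3 points, change SD 3, and the reading in which baseline is carried forward. With equal dropout of 8% to 24%, a true 1.0-point difference shrinks to between 0.92 and 0.76, at little cost in power. With no decline there is no such bias, and for the scales scored more often the effect may be small or absent.

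The primary FDG analysis uses paired scans and is not affected. The change should be made, but nothing here threatens the trial's main conclusion.

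**What to change.** Before unblinding:

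1. In the Synopsis and 11.2, replace LOCF as the main rule with the SAP section 9 models on all randomised subjects, using observed data to Week 24 without carry-forward. Use the same analysis set in both documents.
2. Keep the SAP's ranking: the time-by-treatment slope test is the main analysis and response profiles are the sensitivity analysis. Label LOCF (if kept), observed case and per-protocol as supportive.
3. Enter early-discontinuation scores at their actual time in the continuous-time model. State one visit-window rule for placing them in the response-profile analysis, where time is categorical.
4. State that the mixed model assumes data missing at random and that unweighted GEE for CGIC needs the stronger assumption of missing completely at random.
5. Finalise the SAP with these points and the current scale names in section 3.2.

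The cost is edits to the Synopsis, 11.2 and SAP sections 3.2, 4, 5 and 9; no new visits or data. In the worked example MMSE intervals would be roughly 11% to 19% wider than LOCF would show. With only two time points, the mixed model gains little precision over observed cases for that scale.

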11.3 Subject Populations for Analysis

With a subject population of 10 patients per arm (placebo and treatment), Kadir et al detected a significant increase ($p < 0.05$) in frontal, parietal, and parietotemporal glucose metabolism within the treatment group, and a significant difference between placebo and treatment arms in parietotemporal glucose metabolism (26). The percent changes associated with these increases ranged from 5.5% to 8%. In two different studies of donepezil (27, 28), the change in glucose metabolism was measured in subjects who improved, rather than declined, in cognitive scores. Using region of interest analysis, Shimadai found significant differences ($p < 0.05$) in frontal regions when comparing the ratio of pre-treatment to post-treatment in 7 responders with regard to ADAS-J cog score to that of 4 non-responders. Using voxel-based analyses, Mega et al found a significant difference in anterior cingulate, prefrontal cortex, and parietotemporal cortex between

6 cognitive responders as compared to similar untreated subjects, even after applying a Bonferroni correction for random effects.

Evaluation of the FDG PET scans of 70 mild AD subjects from the Alzheimer's Disease Neuroimaging Initiative (ADNI) database indicates that, based upon mean and standard deviation of glucose metabolism in prefrontal cortex, a change in mean Standardized Uptake Value ratio (SUVr) of 5% could be statistically significant between two independent groups (drug, placebo) at 70% power ($p < 0.05$, two-tailed) with 26 subjects per arm, or at 80% power with 32 subjects per arm. The number of subjects required reduces quickly with effect, as a change of 10% would require only 8 subjects per arm to achieve 80% power if variance within the study group is comparable to that within the mild AD ADNI population (greater variance would increase the number of subjects required or decrease the power). Region of interest evaluation is typically more conservative than voxel-based analysis because effects common across subjects often involve sub-regions and measurement of change may be diluted by the use of broader pre-determined measurement areas. Use of voxel-based approaches, and in addition, multivariate methods and a pattern-based classification approach, are expected to increase statistical power as they improve the signal to noise ratio and are not limited to predefined regions.

11.4 FDG PET Imaging Analysis

11.4.1. Screening Classification

The Screening FDG PET scan of each subject will be evaluated using ADMdx's dementia classifier, to assess whether the subject expresses a pattern consistent with AD or alternatively, that of other dementias. The classifier has developed machine learning methods and a comprehensive set of reference data from ADNI and other sources. The FDG PET scan of a subject will be independently compared to a set of canonical variant patterns that in combination characterize the patterns of relative hypometabolism caused by different types of dementia. A probability will be assigned to determine whether the subject is "AD-like" or better characterized as a different dementia.

In addition, hypometabolism will be assessed in frontal cortex and occipital cortex, and parietal asymmetry checked, to identify possible atypical or comorbid presentations that may impact clinical attributes. The AD-like or non-AD-like status of each subject will be reported back within 7 days of image receipt to allow enrollment decisions.

11.4.2 Screening Characterization

The Screening FDG PET scan of each subject will be evaluated using ADMdx's AD Progression classifier, to assess the subject's disease-related hypometabolism status relative to reference subjects and other study subjects. The FDG PET scan of a subject will be independently compared to a set of canonical variant patterns that in combination characterize the patterns of relative hypometabolism caused by different stages of progression toward AD dementia. This numeric score will be used to project likely cognitive trajectory for comparison to actual results. It can also be used to stratify groups for sub-analyses, creating more homogeneous analysis groups at baseline.

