3.3 Primary Endpoint

The primary study endpoint is the change from screening visit (baseline FDG) to Week 24 in regional glucose metabolism as measured by standardized uptake value ratio (SUV_r) obtained through the FDG-PET.

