There are two FDG-PET scans to be conducted per participant in this study. The scans will be done at the Screening visit for study eligibility, and at Week 24 visit for end of treatment scan and comparison.

The scanning protocol and equipment qualification requirements for this study will be consistent with those implemented in ADNI 2 (30). FDG-PET imaging data will be obtained at two sites: the Cleveland Clinic facilities in Cleveland, Ohio and Las Vegas, Nevada. Each of these sites uses a Siemens Biograph PET/CT LSO 16 slice camera. As part of site qualification, site practices will be reviewed, along with recent equipment calibration logs. If the site has a 3D-Hoffman phantom

scan collected within the past 12 months available, the scan will be provided for examination. If a de-identified patient brain scan can be made available, it will be provided for examination. The requirements for subject management in preparation for the scan, during FDG uptake, and during image acquisition will be reviewed with staff to ensure that these can be met. Since the Cleveland Clinic participates in ADNI as well as numerous other clinical trials, it is anticipated that requirements will be met.

The scanner will have an up-to-date calibration and normalization on the date of each imaging session. A daily QC check will be done at the beginning of the day the scanning will be completed. The scan will be visually inspected for abnormalities. If there is a possibility that the abnormality could impact the PET scan quality, the visit will be rescheduled.

Daily CT quality assurance will be performed as recommended by the specific vendor, and should typically include a "checkup/calibration" procedure and a water phantom scan. The checkup/calibration procedure guarantees optimum image quality by warming up the x-ray tube and should be performed at startup and within 1 hour prior to any scan. The water phantom provides quality measurements of 3 parameters. The parameters are the CRT value of water calculated in Hounsfield units (HU), the pixel noise of images calculated as a standard deviation, and the tube voltages measured directly on the x-ray tubes. These three measurements should be determined for all available kVp values.

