11.4.3 Longitudinal Voxel-based Evaluation

The spatially normalized longitudinal FDG PET scans of each subject will be analyzed using ADMdx's NPAIRS multivariate software. Classes will be defined according to treatment or placebo condition, and visit. Example analyses are shown in Table 1 below. The output of this

evaluation will be a series of patterns showing relative increases and decreases in cerebral glucose metabolism, quantification of the placement of each subject at each time point relative to these patterns of effect, and quantification of the contribution of each pattern to the overall effect. Metrics of reproducibility and predictive power are also provided. At preference of Sponsor, group assignments may be provided in a blinded manner – that is, Group A and Group B, without designation as treatment or placebo. In the table below, to better illustrate the comparisons, they are referred to as Placebo and Treatment, but these may instead be “Group A” and “Group B.”

Table 3. NPAIRS analyses of treatment effect and stratification impact

Analysis	Group	Baseline	6 months
1	Treatment (within group only)	x	x
2	Placebo (within group only)	x	x
3	Treatment	x	x
	Placebo (both in a single analysis)	x	x
4	Treatment – mild subjects	x	x
	Treatment – later stage subjects	x	x
	Placebo – mild subjects	x	x
	Placebo – later stage subjects	x	x
5	Treatment – subjects age 50 - 65	x	x
	Treatment – subjects age >65	x	x
	Placebo – subjects age 50-65	x	x
	Placebo – subjects age >65	x	x

SPM-t contrasts will also be performed of selected groups, at thresholds of $p < 0.005$, and a cluster extent threshold of 25 voxels. These are limited to paired contrasts (e.g., baseline vs. 6 months for treatment group), or to contrasts of the difference images between baseline and 6 months, treatment vs. placebo groups. Information is more limited with regard to individual subject distribution other than at specific voxel locations.

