11.4.4 Longitudinal Region of Interest Evaluation

The SUVr calculated for each subject will be compared using t-tests, within groups and across groups, as shown in Table 4 below. While the pre-identified reference regions for testing will be whole brain, cerebellum, and pons, an alternate reference region may be identified through the use of NPAIRS multivariate analysis and applied.

Table 4 Regions of interest for FDG analysis

Analysis	Change in FDG PET measure:	Dorso-lateral PFC	Striatum	Hip - Med temp	Anterior cingulate	Post cing-precun	Lateral temp	Inferior parietal
1	Treatment: 6m vs. screening	x	x	x	x	x	x	x
2	Placebo: 6m vs. screening	x	x	x	x	x	x	x
3	Change in treatment vs. change in placebo groups	x	x	x	x	x	x	x
4	1, 2, and 3 in substrata for	x	x	x	x	x	x	x

Analysis	Change in FDG PET measure:	Dorso-lateral PFC	Striatum	Hip - Med temp	Anterior cingulate	Post cing-precun	Lateral temp	Inferior parietal
	disease severity and age							

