The subject will be asked to rest comfortably in the room with lights dimmed to a level similar to twilight for 30 minutes for incorporation of [18F]-FDG in the brain. The subject's eyes will be open, away from any direct light, and the ears will remain un-occluded. The participant will be directed to maintain their gaze on a constant object throughout the uptake period. This point of focus (object) should be the same across subjects and across scans. The subject should also be instructed to avoid any motion, foot tapping, or other variable activity. Comfort should be assured in order to reduce the likelihood of movement. The participant must be monitored frequently to be certain of compliance and to ensure that the eyes do not close and they remain awake. It is important that no sudden noises or environmental changes occur within or just outside of the participant's room during [18F]-FDG uptake.

Just prior to injection, and at the end of the uptake period, the subject will be asked to answer a short set of questions regarding their affect. The clinician will also be asked to note the subject's affect, and particularly whether the subject exhibits signs of agitation, somnolence, or depression. These observations are important because differences between scanning sessions in the patient's affect can impact measured signal, creating confounds in the measurement of treatment effects. If a subject is notably agitated, the process should not

begin until that agitation can be alleviated. If this is not reasonably achievable, the scan should be rescheduled.

At the end of the 30-minute incorporation period, the participant will be encouraged to use the restroom to empty their bladder. Ample time will be given to ensure that the participant will be on the scanner and ready for data acquisition to begin at 30 minutes post-injection.

(iii) Image Acquisition

The participant will be positioned and secured in the scanner. Proper participant positioning and the prevention of subject motion during acquisition is critical for a reliable PET scan. Excessive motion between the emission scan and the CT scan used for attenuation correction is the single most common cause of failed studies. For this reason, the protocol includes several steps to reduce the likelihood of movement, as follows, and consistent with ADNI guidelines.

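### If severity strata are formed from the AD Progression score, within-arm FDG change tests in those strata carry regression to the mean, because score and baseline come from one scan

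*Protocol*

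**What the plan says.** Protocol 11.4.2 describes the AD Progression classifier. It begins "The Screening FDG PET scan of each subject will be evaluated using" that classifier, and says of the resulting score: "It can also be used to stratify groups for sub-analyses, creating more homogeneous analysis groups at baseline". SAP 8.2 repeats this.

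Protocol 3.3 defines the primary endpoint as the "change from screening visit (baseline FDG) to Week 24 in regional glucose metabolism". Protocol 9.10 confirms that no separate baseline scan exists: "There are two FDG-PET scans to be conducted per participant in this study", one at screening and one at Week 24.

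Under Protocol 11.4.4 the SUVr values are "compared using t-tests, within groups and across groups", with no baseline adjustment. In Table 4, rows 1 and 2 are the within-arm comparisons of six months with screening, and row 3 compares the change between arms. Row 4 repeats "1, 2, and 3 in substrata for" disease severity and age, over seven regions. Table 3 in 11.4.3, titled "NPAIRS analyses of treatment effect and stratification impact", has an analysis 4 with mild and later-stage classes in both arms. The same section allows paired SPM contrasts in selected groups.

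Neither table names the severity variable or a cut-point, and SAP 8.2 to 8.4 do not settle it.

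**The concern.** A patient can fall in the later-stage group partly because the screening scan happened to read low. At Week 24 that error is replaced by a fresh one, so such patients read higher on average with no drug effect. The mild group moves the other way. Grouping on a noisy scan makes the groups alike at that scan only.

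Scan-day variation is a recognised issue here. Appendix A says that differences in a patient's affect between sessions "can impact measured signal, creating confounds in the measurement of treatment effects". Its controls on the uptake period should reduce this variation, but cannot be assumed to remove it.

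At stake is a false message about stage. In the rasagiline arm, later-stage patients could seem to hold up better than mild patients purely through measurement error. Within-arm results may be given weight, since Protocol 11.3 cites a significant within-treatment-group increase in an earlier trial as support for the design. In a proof-of-concept trial, such a pattern could influence the population chosen for the next study.

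**Working it through.** **1. The plan's own figures, and the SD.** Protocol 11.3 gives, for a 5% SUVr difference at two-sided 0.05, 26 per arm (70% power) or 32 per arm (80%), and 8 per arm for a 10% difference (80%). The SD is not stated. From 32 per arm, SD = 5 × √(32/2) / (1.960 + 0.842) = 20 / 2.802 = 7.14% of the mean. That SD returns 2 × (1.960 + 0.524)² × 7.14² / 5² = 25.2, so 26 per arm at 70%, and 32/4 = 8 per arm for 10%. The stated figures agree with each other; this does not verify the SD. I use 7.1%.

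**2. Size of the shift.** Assumptions, none given in the documents: a median split (about 12 of the 25 per arm in each stratum), scan reliability R of 0.80 to 0.95, and no true change. In general,

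shift = 0.798 × cov(score, region's screening error) / SD(score),

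where 0.798 is the mean of a half-normal variable. If the score picks up a region's scan error in the same proportion as its true level, and correlates c with that region's screening SUVr, this becomes

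shift = 0.798 × SD × (1 − R) × c.

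For R = 0.80 and c = 1: 0.798 × 7.1 × 0.20 × 1 = 1.13%. The table gives the upward shift in the later-stage stratum, with the simulated chance of a falsely significant rise in brackets (paired t-test, 20,000 runs, nominal 2.5%):

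| R | c = 0.5 | c = 0.7 | c = 1 |
|---|---|---|---|
| 0.80 | 0.57% (6.3%) | 0.79% (8.2%) | 1.13% (13.3%) |
| 0.90 | 0.28% (4.9%) | 0.40% (6.1%) | 0.57% (8.4%) |
| 0.95 | 0.14% (3.9%) | 0.20% (4.6%) | 0.28% (5.9%) |

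The mild stratum shifts down by about the same amount. At c = 0 there is no shift.

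**3. A score that pools regions.** The classifier uses a multi-region pattern, which dilutes one region's error. Suppose the score averages seven regions with independent errors and true levels correlated 0.8 (assumed). The formula becomes

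shift = 0.798 × SD × [(1 − R)/7] / √{R × (1 + 6 × 0.8)/7 + (1 − R)/7}.

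- R = 0.80: 5.666 × 0.0286 / 0.832 = 0.19%.
- R = 0.95: 5.666 × 0.00714 / 0.891 = 0.05%.

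The false-rise rate is then about 3 to 4%. Error shared across regions moves the result back towards the table. Over the whole assumed range of shared error, the shift is about 0.05 to 1.1% and the false-rise rate about 3 to 13%.

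**4. With true decline.** Assume a decline of 1.5% over 24 weeks (the documents give no figure) and c = 0.7. Simulated mean changes:

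| R | Later-stage | Mild | Gap |
|---|---|---|---|
| 0.80 | −0.7% | −2.2% | 1.5 points |
| 0.90 | −1.1% | −1.9% | 0.8 points |
| 0.95 | −1.3% | −1.7% | 0.4 points |

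A falsely significant rise now occurs in at most about 1.4% of tests at any setting, but the gap between stages remains.

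**5. Between-arm contrast.** Within a score-defined later-stage stratum (R = 0.80, c = 1), the simulated treatment-minus-placebo difference in change was about 0.03% and the type I error 5.05%. Both arms shift equally, so the bias cancels.

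**6. A stratifier that does not share the scan's error.** The mean shift is about 0 in both strata, and each tail rejects at about 2.5%.

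**The case against.** Five points can be made on the other side.

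- **The use is optional.** A reader might infer that the plan commits to cutting strata on this score. It does not: the wording is permissive, 11.4.3 calls its analyses examples, and MMSE could define severity under the present text. This stands, so the point is conditional. It does not remove it, because the within-arm stratum tests are planned and the only stratifier named for them shares the baseline's error.
- **The size rests on shared scan error, not on overall correlation.** This stands. A pooled score can correlate highly with a region and still cause little shift (step 3). The documents give no figure, so the range is wide and its lower end is negligible.
- **Later-stage patients need not appear to improve.** A reader might infer an apparent gain. Protocol 2.3 reports that decline is fastest in AD, and a modest true decline outweighs the shift (step 4). What survives is a false difference between stages.
- **No mild-versus-later-stage test is listed.** Table 4 row 4 repeats only the two within-arm tests and the between-arm test. An inflated error rate for a direct test between strata would concern an analysis that is not planned. The risk lies in reading the stratum results side by side.
- **The control arm is present.** Table 3 analysis 4 includes the placebo strata, and Table 4 row 4 includes the between-arm contrast. This stands, and confines the problem to conclusions drawn within one arm.

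**Conclusion.** The concern holds conditionally. If the AD Progression score forms the severity strata, the within-arm tests in Table 4 row 4, and any paired SPM contrasts in those strata, are biased upward for later-stage and downward for mild patients. Against the 5% difference used for sample size, a shift of about 0.05 to 1.1% per stratum is small to modest. The false-rise rate of 3 to 13% applies per region with no true change.

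These figures rest on the back-solved SD and on assumed reliability, shared error and a median split. A reader might take this as a threat to the primary result. It is not: the primary comparison and the treatment-versus-placebo contrast within strata are unbiased, so only secondary subgroup findings are affected. It is still worth correcting, because the remedy is nearly free.

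**What to change.** In Protocol Table 3 analysis 4, Table 4 row 4 and SAP 8.2 to 8.4, take one of two routes:

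1. Define disease severity by a measure not derived from the screening FDG scan, such as screening MMSE, which is already collected, and fix the cut before unblinding.
2. If the AD Progression score is kept, state that conclusions in those strata come only from row 3 (change in treatment against change in placebo), and not from within-arm rows 1 and 2.

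The cost is wording in the two documents, with no new data, visits or patients. The downside is small. Under route 1, MMSE follows metabolic severity less closely than an FDG score. Under route 2, the within-arm stratum results become descriptive only.
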